1.2.2 Metformin (Met)

Metformin is an oral antihyperglycemic agent that reduces plasma glucose levels by decreasing intestinal glucose absorption and hepatic glucose production and enhancing the glucose uptake and utilization of peripheral tissue. Thus, metformin renders a reduction of basal and postprandial plasma glucose in patients with T2DM. Unlike sulfonylureas (e.g. glyburide) metformin does not increase insulin secretion and is not associated with hypoglycaemia in either patients with T2DM or healthy volunteers [R11-4761].

The absolute bioavailability of metformin is 50-60 % under fasting conditions. The intake of food decreases the extent of absorption. A 40% lower C_{max} and a 25% lower AUC (area under the curve) were reported following a single dose administration of 850 mg metformin with food. Studies using single oral doses of 500 - 1500 mg metformin indicate that there is a lack of dose proportionality with increasing doses, which is due to decreased absorption rather than an alteration in elimination [R10-5341].

Metformin is negligibly bound to plasma proteins. The drug partitions into erythrocytes, which might represent a deep compartment of distribution. Intravenous studies in healthy volunteers demonstrate that metformin is excreted unchanged in the urine and neither undergoes hepatic metabolism nor biliary excretion. Following oral administration approximately 90% of the absorbed drug is eliminated via the renal route with a plasma-elimination half-life of about 6.2 hours [R10-5341].

Metformin is available as tablets for oral administration in the strengths 500, 850 and 1000 mg [R10-5341]. The maximum recommended daily dose is 3000 mg in adults [R11-4761].

In a double-blind, placebo-controlled US clinical trial involving obese patients with type 2 diabetes whose hyperglycaemia was not adequately controlled with diet alone, treatment with metformin (up to 2550 mg/day) for 29 weeks resulted in significant mean net reductions in FPG, PPG and HbA1c of 59 mg/dl, 83 mg/dl, and 1.8 %, respectively, compared to the placebo group [R10-5341].

Metformin was well tolerated by healthy male volunteers given alone (1000 mg twice daily) and in combination with empagliflozin (50 mg once daily) for 5 days [U09-1852-01]. The most frequently reported adverse events were headache, diarrhoea and nausea which were considered drug related adverse events. The incidence of these events on empagliflozin + metformin did not exceed the incidence observed under metformin monotherapy. Gastrointestinal side effects such as abdominal pain, diarrhoea and nausea represent well-known side-effects of metformin [R11-4761]. Hypoglycaemic events did not occur in any

<c12345678-01> Trial Protocol Page 21 of 76

Proprietary confidential information © 2021 Boehringer Ingelheim International GmbH or one or more of its affiliated companies

treatment period. The pharmacokinetics of empagliflozin and metformin were similar following co-administration compared to both monotherapies alone [U06-1897-08].

1.2.1 Residual Effect Period

The Residual Effect Period (REP) of Empa is 4 days. This is the period after the last dose with measurable drug levels and/or pharmacodynamic effects is still likely to be present.

The Residual Effect Period (REP) of Met is 3 days. This is the period after the last dose with measurable drug levels and/or pharmacodynamic effects is still likely to be present.

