3.3.4 Withdrawal of subjects from treatment or assessments

Subjects may discontinue trial treatment or withdraw consent to trial participation as a whole ('withdrawal of consent') with very different implications; please see sections 3.3.4.1 and 3.3.4.2 below.

If a subject is removed from or withdraws from the trial prior to the first administration of trial medication, the data of this subject will not be entered in the case report form (CRF) and will not be reported in the clinical trial report (CTR). If a subject is removed from or withdraws from the trial after the first administration of trial medication, this will be documented and the reason for discontinuation must be recorded in the CRF; in addition, the data will be included in the CRF and will be reported in the CTR. At the time of

number: PBDS004/21

Proprietary confidential information © 2021 Boehringer Ingelheim International GmbH or one or more of its affiliated companies

discontinuation, a complete end of trial examination will be performed, if possible, and the information will be recorded in the CRF. If the discontinuation occurs before the end of the REP (see Section 1.2.3), the discontinued subject should if possible be questioned for AEs and concomitant therapies at or after the end of the REP in order to ensure collection of AEs and concomitant therapies throughout the REP, if not contrary to any consent withdrawal of the subject.

If it is known that a subject becomes pregnant during the trial, administration of the trial medication is to be stopped immediately, and the subject is to be removed from the trial. The subject is to be followed until she has given birth or until the end of the pregnancy. The subject's data are to be collected until the end of the trial (last visit of last subject) and reported in the CTR. For reporting of pregnancy and associated events, refer to Section 5.2.6.2.4.

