4.2 OTHER TREATMENTS, EMERGENCY PROCEDURES, RESTRICTIONS

4.2.1 Other treatments and emergency procedures

There are no special emergency procedures to be followed. No additional treatment is planned. However, if adverse events require treatment, the investigator can authorise symptomatic therapy. In those cases, subjects will be treated as necessary and, if required, kept under supervision at the trial site or transferred to a hospital until all results of medical evaluations are acceptable.

is equipped with an emergency room, defibrillators, mobile resuscitation apparat, a 24-hour ICU ambulance and an ICU bed in major hospital 4 km distant.

During confinement, in each study period, the participants will be followed by the healthcare professionals during all the period viewing the detection of adverse events, including signs of toxicity.

The participants will be instructed about the potential adverse events, as well as the need to inform them immediately to the investigator or his/her team.

Each participant will be requested to report any adverse event symptoms and it has occurred. The medical team will also be requested to notify the principal investigator if the use of additional medication has been required.

The questions performed to know if the participant has had some adverse event must be limited to general questions, such as: How are you?

Any adverse events occurring after hospitalization must be immediately informed to the team by any mean (telephone, personally, e-mail, etc.).

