5.2.5.2 Adverse event collection and reporting

5.2.5.2.1 AE collection

Upon enrolment into a trial, the subject's baseline condition is assessed (for instance, by documentation of medical history/concomitant diagnoses), and relevant changes from baseline are noted subsequently.

Subjects will be required to report spontaneously any AEs as well as the time of onset, end time, and intensity of these events. In addition, each subject will be regularly assessed by the medical staff throughout the clinical trial and whenever the investigator deems necessary. As a minimum, subjects will be questioned for AEs (and concomitant therapies) at the time points indicated in the Flow Chart. Assessment will be made using non-specific questions such as 'How do you feel?'. Specific questions will be asked wherever necessary in order to more precisely describe an AE.

A carefully written record of all AEs shall be kept by the investigator in charge of the trial. Records of AEs shall include data on the time of onset, end time, intensity of the event, and any treatment or action required for the event and its outcome.

The following must be collected and documented on the appropriate CRF(s) by the investigator:

- From signing the informed consent onwards until an individual subject's end of trial:
 - o All AEs (serious and non-serious) and all AESIs
 - The only exception to this rule are AEs (serious and non-serious) and AESIs in Phase I trials in healthy volunteers, when subjects discontinue from the trial due to screening failures prior to administration of any trial medication. In these cases, the subjects' data must be collected at trial site but will not be entered in the CRF or trial database and will not be reported in the CTR.
- After the individual subject's end of trial:
 - The investigator does not need to actively monitor the subject for AEs but should only report any occurrence of cancer and related SAEs and related AESIs of which the investigator may become aware of by any means of communication, e.g. phone call. Those AEs should, however, not be reported in the CRF.

Page 48 of 76

Boehringer Ingelheim BI Trial No.: 1276-0041

number: PBDS004/21 <c12345678-01> Trial Protocol

Proprietary confidential information © 2021 Boehringer Ingelheim International GmbH or one or more of its affiliated companies

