7. INVESTIGATIONAL PLAN

7.1 VISIT SCHEDULE

Exact times of measurements will be documented. The acceptable time windows for screening and the end of trial examination are provided in the Flow Chart.

Study measurements and assessments scheduled to occur 'before' trial medication administration on Day 1 are to be performed and completed within a 2 h-period prior to the trial drug administration.

The acceptable deviation from the scheduled time for vital signs, ECG, and laboratory tests will be \pm 30 min.

If scheduled in the Flow Chart at the same time as a meal, vital signs, and 12-lead ECG recordings, blood sampling, have to be done first..

For planned blood sampling times, refer to the Flow Chart. While these nominal times should be adhered to as closely as possible, the actual sampling times will be recorded and used for the determination of pharmacokinetic parameters. If a subject misses an appointment, it will be rescheduled if possible.

DETAILS OF TRIAL PROCEDURES AT SELECTED VISITS

7.2

Screening

After having been informed about the trial, all subjects will provide written informed consent in accordance with GCP and local legislation prior to enrolment in the study.

For information regarding laboratory tests (including drug and virus screening), ECG, vital signs, and physical examination, refer to Sections 5.2.3 to 5.2.5.

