7.2.1 Treatment periods

Each subject is expected to participate in 2 treatment periods (2 Days before treatment -2,-1 and Days 1, 2, 3, and 4 in each period). At least 7 days will separate drug administrations in the first and second treatment periods.

On Day -1 of each treatment period, study participants will be admitted to the trial site and kept under close medical surveillance for at least 12 h following drug administration. The subjects will then be allowed to leave the trial site after formal assessment and confirmation of their fitness. On all other study days, subjects will be treated in an ambulatory fashion.

For details on time points and procedures for collection of plasma samples for PK analysis, refer to Flow Chart and Section 5.3.2.

The safety measurements performed during the treatment period are specified in Section 5.3 of this protocol and in the Flow Chart. For details on times of all other trial procedures, refer

number: PBDS004/21

<c12345678-01> Trial Protocol Page 62 of 76

Proprietary confidential information © 2021 Boehringer Ingelheim International GmbH or one or more of its affiliated companies

to the Flow Chart. AEs and concomitant therapy will be assessed continuously from screening until the end of trial examination.

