7.2.2 Follow-up period and trial completion

For AE assessment, laboratory tests, recording of ECG and vital signs, and physical examination during the follow-up period, see Sections 5.2.2 to 5.2.5. Subjects who discontinue treatment before the end of the planned treatment period should undergo the EoTrial Visit.

All abnormal values (including laboratory parameters) that are assessed as clinically relevant by the investigator will be monitored using the appropriate tests until a return to a medically acceptable level is achieved. (S)AEs persisting after a subject's EoTrial Visit must be followed until they have resolved, have been sufficiently characterised, or no further information can be obtained.

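### Minor, safety completeness only: on the Flow Chart's own Day scale, a completer's end-of-trial examination can close adverse event collection up to about one day before the stated 4-day empagliflozin residual effect period ends

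*Combined protocol and SAP*

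**What the plan says.** - **Residual effect period (REP).** Section 1.2.1 (Residual Effect Period) says "The Residual Effect Period (REP) of Empa is 4 days". It defines the REP as running from the last dose and covering measurable drug levels or pharmacodynamic effects. The metformin REP is 3 days.
- **Window.** The FU row of the Flow Chart places the end-of-trial examination on Day 4 to 14, with no planned time and no clock time. Section 7.1 makes this binding: "The acceptable time windows for screening and the end of trial examination are provided in the Flow Chart".
- **Day scale.** Within a treatment period the Flow Chart doses on Day 1 at about 07:00 and puts the 24, 48 and 72 h visits on Days 2, 3 and 4.
- **End of AE collection.** Section 7.2.1: "AEs and concomitant therapy will be assessed continuously from screening until the end of trial examination". Section 5.2.5.2.1 collects all AEs in the CRF "From signing the informed consent onwards until an individual subject's end of trial". After that there is no active monitoring. The investigator reports only cancers, related serious adverse events (SAEs) and related adverse events of special interest (AESIs) that come to notice, and "Those AEs should, however, not be reported in the CRF".
- **Aim of covering the REP.** Section 3.3.4 asks that a subject who discontinues before the REP is over be questioned at or after its end "in order to ensure collection of AEs and concomitant therapies throughout the REP". The request applies only to discontinued subjects and is qualified by feasibility. Nothing equivalent is stated for completers.

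**The concern.** The REP is the protocol's own statement of how long a drug effect may still be present. If a completer's last AE enquiry can come before the REP is over, an event that starts in the remaining hours has no route into the CRF unless the subject is still under collection. Under Section 5.2.5.2.1 the events lost would be new non-serious AEs, and SAEs or AESIs judged unrelated. A subject who discontinues could then have fuller coverage of the REP than one who completes both periods and is examined on Day 4.

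Only the completeness of the safety data is at stake. The pharmacokinetic endpoints come from plasma samples up to 72 h and do not depend on when the end-of-trial examination takes place.

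**Working it through.** **Inputs.** Dose on Day 1 at about 07:00, 72 h visit on Day 4, and end-of-trial window Day 4 to 14 (Flow Chart). Empagliflozin REP 4 days and metformin REP 3 days after the last dose (Section 1.2.1, Residual Effect Period). Terminal empagliflozin half-life 10 to 19 h (Clinical pharmacokinetics under the empagliflozin drug profile).

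**Step 1: the Flow Chart's scale.** Day 1 07:00 + 72 h = Day 4 07:00, which agrees with the chart's own Day 4 entry for the 72 h visit.

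**Step 2: end of the REP.** Empagliflozin: 4 × 24 = 96 h, so Day 5 at 07:00. Metformin: 3 × 24 = 72 h, so Day 4 at 07:00. An examination at or after the 72 h sample therefore covers metformin.

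**Step 3: gap = 96 h − time of the examination after the dose.**

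| Examination | Hours after dose | Gap (h) |
|---|---|---|
| Day 4, 07:00 (nominal 72 h) | 72 | 24 |
| Day 4, 08:00 (clock time printed for that visit) | 73 | 23 |
| Day 4, 17:00 | 82 | 14 |
| Day 4, midnight | 89 | 7 |
| Day 5, 07:00 or later | 96 or more | 0 |

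The ±1 h tolerance on the 72 h sample (Section 6.5.2.1) moves the largest figure to 25 h if that sample is taken early. Clock times are approximate and the REP is given in whole days, so about one day is as precise as the result should be put.

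**Step 4: how much of the window is affected.** Days 4 to 14 are 14 − 4 + 1 = 11 days. Only Day 4 lies wholly before the REP ends. The documents do not show how often it would be used.

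**Step 5: alternative readings.**
- Follow-up days counted from the last dose: earliest examination at 4 × 24 = 96 h, gap 0.
- REP counted as calendar Days 1 to 4: it ends at midnight on Day 4 (89 h), so a 07:00 examination that day is still 89 − 72 = 17 h early.

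**Step 6: rough exposure in the gap.** Assume simple exponential decay from dosing with half-life *h*.
- Fraction remaining at 72 h is 2^(−72/h): 0.7% for h = 10 and 7.2% for h = 19.
- Share of 0–96 h exposure falling in 72–96 h is (2^(−72/h) − 2^(−96/h)) / (1 − 2^(−96/h)): 0.55% for h = 10 and 4.35% for h = 19.

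These figures are illustrative. The protocol describes a biphasic decline, and its REP also covers pharmacodynamic effects, which this calculation does not capture.

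**The case against.** **The day count is not settled.** The FU row is a separate visit with no planned time. The Day column is not one continuous scale either: screening days refer to the first dose, and Days −2 to 4 restart in each period. Day 4 of follow-up could mean four days after the last dose, and then nothing is wrong. This stands as a condition on the finding. The treatment-period scale is still the more natural reading, because the only other post-dose Day 4 in that column is the 72 h visit. Table 5.2.3: 1 adds to the doubt: it assigns the end-of-trial examination to Visit 3, whereas the Flow Chart uses Visit 4.

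**No commitment to completers is broken.** A reader might infer that the protocol promises AE collection over the whole REP for everyone and then contradicts itself. The documents do not support that. The aim in Section 3.3.4 concerns subjects who leave early, and even there it is conditional. No section extends it to completers, and no planned analysis shown uses a REP-based AE period. What remains is an aim stated for one group and left open for the other.

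**Other provisions cover most of the risk.** AEs are asked about at 24, 48 and 72 h and at the end-of-trial examination. Section 4.2.1 tells participants that "Any adverse events occurring after hospitalization must be immediately informed to the team by any mean", with no end date. Under Section 7.2.2, events persisting after the last visit "must be followed until they have resolved, have been sufficiently characterised, or no further information can be obtained". Related SAEs, related AESIs and cancers that become known are still reported. All of this reduces the consequence. However, follow-up of persisting events does not capture new ones, and a participant's later report of a new non-serious or unrelated event has no CRF entry under Section 5.2.5.2.1.

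**Conclusion.** The point holds as a minor, conditional one. On the Flow Chart's treatment-period scale, the plan allows a completer's AE collection to close up to about one day before the stated empagliflozin REP ends, on one of 11 permitted days. What could be missed is new non-serious AEs, and SAEs or AESIs judged unrelated, that start in that interval. Few are to be expected.

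This rests on four assumptions:
- the follow-up days use the same scale as the rest of the Day column;
- 4 days means 96 h from dosing;
- the examination is not done before the 72 h sample;
- the individual subject's end of trial is the end-of-trial examination, as Section 7.2.1 implies (Section 9.6 defines only the end of the whole trial).

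If the first assumption fails, the gap is zero.

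A reader might also infer that completers in general will be closed out early, or that the bioequivalence conclusion is weakened. Neither is supported: the documents do not show that Day 4 would be used at all, and the primary endpoints, power and sample size do not depend on this window.

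**What to change.** Reconcile the end-of-trial window (Flow Chart, Section 7.1) and the AE collection period (Sections 5.2.5.2.1 and 7.2.1) with the REP in Section 1.2.1 and the aim in Section 3.3.4, so that AE collection for completers also spans the stated REP. This can be done through the start of the window or through one AE contact for subjects examined before the REP ends. State in the Flow Chart whether the follow-up days count from Day 1 of Period 2 or from the last dose. If the latter was intended, that sentence alone removes the gap.

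The cost is protocol wording and, for the few subjects who would otherwise be examined early, a slightly later visit or one contact. Treatment, sampling, analysis and sample size do not change.

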1.3 RATIONALE FOR PERFORMING THE TRIAL

Combination drug therapy should improve compliance and provide additive glycaemic control. This can be achieved by combining drugs with different mechanisms of action which work together to have an additive or synergistic antidiabetic effect. Providing both ingredients in a single tablet will help facilitate drug dosing and compliance for patients. The actual BE study is performed as per local regulatory requirement of ANVISA in Brazil as a pre-requisite for local regulatory approval of the empagliflozin/metformin JardianceDuo fixed dose combinations.

1.4 BENEFIT - RISK ASSESSMENT

Participation in this bioequivalence study is without any (therapeutic) benefit for healthy subjects. Their participation in the study, however, is of major importance for the technical validation of the oral fixed dose combination of two antidiabetic principles, empagliflozin and metformin. Subjects are exposed to risks of study procedures and risks related to the exposure to the trial medication.

Procedure-related risks

The use of an indwelling venous catheter for the purpose of blood sampling may be accompanied by mild bruising and, in rare cases, by transient inflammation of the wall of the vein. After initial irritation, the presence of an indwelling cannula is usually painless and hardly noticeable. In addition, in rare cases a nerve might be injured while inserting the venous catheter, potentially resulting in paraesthesia, reduced sensibility, and/or pain for an indefinite period. The same risks apply to venepuncture for blood sampling.

The total volume of blood withdrawn per patient during the entire study will not exceed 500 mL.

Drug-related risks and safety measures

number: PBDS004/21

<c12345678-01> Trial Protocol Page 22 of 76

Proprietary confidential information © 2021 Boehringer Ingelheim International GmbH or one or more of its affiliated companies

Empagliflozin: The overall safety profile of empagliflozin is favourable for human studies at chronic doses up to 100 mg/day. The maximum dose administered in the single rising dose study was 800 mg and was well tolerated.

In studies with healthy subjects, the overall adverse event rate with empagliflozin was 32.4%, 20.3 % with placebo and 24.0% with the comparator groups. One volunteer had a serious adverse event (migraine with aura) that required hospitalization, this event was not assessed to be drug related. The most frequent adverse events (>2%) comprise headache (12.1 %), nasopharyngitis (4.4 %), diarrhea (3.8 %) and nausea (3.1 %). Except for headache (5.1 % in placebo) none of these AEs occurred with placebo while various comparators (e.g. metformin) had equivalent or greater incidences of these AEs [U06-1897-08].

In the present study subjects are exposed to 1 single dose of 10 mg of empagliflozin plus 850 mg of metformin and 1 single dose of 12,5mg empagliflozin plus 850 mg metformin fixed dose combination, which are separated by a wash-out phase of 1 week. Based on the previous experience with empagliflozin the safety risk to healthy subjects related to the intake of empagliflozin in this trial is expected to be low.

Metformin: Most frequent adverse events of metformin are [R11-4761]:

>10 %: gastrointestinal disorders (nausea, vomiting, diarrhoea, stomach ache)

1-10 %: changes in taste

< 0.01 %: skin reactions (erythema, itching, urticaria), abnormal liver function test

In diabetic patients, the intake of metformin can cause lactic acidosis in very rare cases (< 0.01%). Risk factors for developing a lactic acidosis are renal insufficiency, impaired hepatic function, excessive alcohol intake, vigorous physical activity and heavy fasting. Until now a lactic acidosis has not occurred in healthy volunteers. Renal and liver function will be checked thoroughly as part of the screening. Alcoholic beverages and unusual physical activities are restricted during the study (see Section 4.2.2).

Gastrointestinal disorders usually occur at the beginning of a metformin therapy. Therefore, they are likely to be expected also after single dose administration of metformin in this trial, which is in line with the observations in other metformin trials. These adverse events are well characterized, disappear within a short period of time and do not represent any safety risk.

Empagliflozin+Metformin: In a pilot trial the relative bioavailability of a 12.5 mg empagliflozin/1000 mg metformin fixed dose combination tablet was compared to the respective single tablets in 16 healthy volunteers. The most frequent adverse event was diarrhea, which occurred in 6 subjects (mild intensity, drug related in each case). The second most frequent reported adverse event was headache (reported by 2 subjects), which was assessed to be drug related in one case. No further drug related AEs occurred [U11-1763-01].

To compare the pharmacokinetics of FDC tablets of empagliflozin/metformin with individual tablets taken together, three randomized, open-label studies were performed with healthy subjects received a single FDC tablet of empagliflozin/metformin in one of six dose combinations: empagliflozin 5 mg or 12.5 mg and metformin 500 mg, 850 mg or 1,000 mg in one period and the individual tablets are taken together under fed conditions in another

number: PBDS004/21

Proprietary confidential information © 2021 Boehringer Ingelheim International GmbH or one or more of its affiliated companies

period. Bioequivalence was also established under fasted conditions for empagliflozin 12.5 mg/metformin 1,000 mg FDC versus individual tablets taken together. Empagliflozin/metformin FDC tablets were found to be bioequivalent to individual tablets taken together at all tested dose strengths and in both fed and fasted conditions¹.

Although rare, a potential for drug-induced liver injury (DILI) is under constant surveillance by sponsors and regulators. Therefore, this trial requires timely detection, evaluation, and follow-up of laboratory alterations in selected liver laboratory parameters to ensure subjects' safety; see also section 5.2.6.1.4, adverse events of special interest.

Overall assessment

In this study two antidiabetic principles are combined. However, neither the use of metformin nor of empagliflozin is associated with hypoglycaemic events which can be explained by their mode of action. Also, no hypoglycaemic signs and symptoms were observed in previous studies investigating the combination of both drugs in healthy subjects. Therefore, a regular measurement of blood glucose is not considered necessary during the present study. This will be done at any time, if clinical signs or symptoms of hypoglycaemia occur.

The volunteers in this study receive no direct medical benefit from participation in this study. Safety will be ensured by the monitoring of subjects for adverse events clinically and verbally. If the investigator should have a clinical concern, the safety of the volunteers will be paramount.

Overall, the risk for subjects participating in this trial is considered to be low and acceptable. Because of the anticipated benefit that a successful clinical development of the FDC tablet could provide to patients with type 2 diabetes the sponsor feels the benefit of a successful clinical development of fixed dose combination tablet to outweigh the risk.

The total volume of blood withdrawn per subject during the entire study will not exceed the volume of a normal blood donation (500 mL). No health-related risk to healthy subjects is expected from withdrawal of this volume of blood.

<c12345678-01> Trial Protocol Page 24 of 76

Proprietary confidential information © 2021 Boehringer Ingelheim International GmbH or one or more of its affiliated companies

